## **4 STUDY OBJECTIVES AND OUTCOME MEASURES**

## 4.1 Primary Endpoints

1. Safety: The primary endpoint will be the percentage of subjects reporting severe (CTCAE v5.0 grade  $\geq$ 3) adverse event (AE) or serious adverse event (SAE), when treated with sirolimus (TAVT-18). Additional safety-related endpoints include:

- a. Percentage of subjects that reduce or discontinue treatment due to an AE or SAE (any grade).
- b. Number of days treatment is withheld due to an AE or SAE (any grade).

2. *Efficacy*: The primary endpoint for efficacy will be time to seizure onset, when treated with sirolimus (TAVT-18). Additional efficacy-related endpoints include:

- a. Age at time of seizure onset
- b. Percentage of subjects with infantile spasms (past or current) at the end of the treatment period (12 months of age).
- c. Seizure frequency at the end of the treatment period (12 months of age).

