## **8 SELECTION AND WITHDRAWAL OF SUBJECTS**

Evaluable subjects are those who have initiated treatment with sirolimus, complete the initial

Version: 7.0\_11May2022

follow-up visit 1 month after initiating treatment, and complete the final assessment at 12 months of age.

Male and female TSC infants 0-6 months of age will be enrolled. There will be no exclusion based on race or sex.

Subjects will be recruited through the TSC clinics which are geographically distributed to allow nationwide recruitment, supplemented by and in partnership with the advocacy organization Tuberous Sclerosis Alliance (TS Alliance) website, *Perspective* magazine, and social media efforts (Facebook and Inspire, online community support page). We will continue existing strategies to improve recruitment and retention that have been successful in our TACERN and PREVeNT studies of TSC infants, which have been able to recruit a similar number of TSC infants under 12 months of age over a similar time period proposed for the current study. Successful recruitment strategies utilized in the past and continued here include leveraging existing outreach and clinical support programs at each center, financial support when available for qualified travel expenses, scheduling visit times and places that accommodate the needs of the family, providing regular feedback to families about the ongoing progress of their children, and optimization of overall TSC clinical medical care.

We may modify recruitment strategies as needed if the current pandemic or other events affect the ability for subjects to travel or willingness to be seen at a research site on schedule or if protocol-required assessments/procedures cannot be performed in a validated manner. Telehealth for clinical assessment of subjects, local collection of sirolimus levels and safety laboratory studies, and increased use of parent-reported measures or personal protective equipment/physical distancing-friendly tools are such strategies in current use by other TSC studies during the COVID-19 pandemic.

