After treatment initiation, follow-up PK assessment and dose-adjustment visits will take place at defined intervals. During Stage 1, scheduled follow-up PK assessment and dose-adjustment visits will occur on day 7 and day 14. Thereafter, PK assessment and dose-adjustment visits will in conjunction with in-person clinic visits (+1 month after treatment initiation and then according to chronological age (3, 6, 9, and 12 months)). During Stage 2, scheduled follow-up PK assessment and dose-adjustment visits will occur 7-14 days after treatment initiation then in conjunction with in-person clinic visits (+1 month after treatment initiation and then according to chronological age (3, 6, 9, and 12 months)). Scheduled PK assessment and dose-adjustment visit will occur 7-14 days after treatment visit windows 7-14 days after treatment initiation are +/- 1 week. All other scheduled PK assessment and dose-adjustment visit windows are +/- 2 weeks from the scheduled visit date, and if the +1 month PK-a visit and the next defined age interval follow-up visits are within 4 weeks of each other, they may be combined into a single study visit. For both Stage 1 or Stage 2, unscheduled PK assessment and dose-adjustment visits will occur 7-14 days after TAVT-18 (sirolimus) dose is adjusted in accordance to protocol to achieve target blood trough level of 10 ng/ml (see section 9.1 above) or due to AE/SAE (see section 12 below).

Procedure	Screening/Baseline (0-6 months of age)	+7-14 days	+1 month	Age: 3 months	Age: 6 months	Age: 9 months	Age: 12 months	Age: 24 months
Eligibility/ Informed Consent	Х							
Baseline History/Demographics	Х							
Interval Medical History			Х	Х	Х	Х	Х	Х
Safety Laboratory tests 	Х		Х	Х	Х	Х	Х	
Sirolimus level 		Х	Х	Х	Х	Х	Х	
Vital Signs	Х		Х	Х	Х	Х	Х	Х
Clinical Exam	Х		Х	Х	Х	Х	Х	Х
Adverse Event Review	Х		Х	Х	Х	Х	Х	
Seizure Diary Review			Х	Х	Х	Х	Х	
EEG 	Х		Х	Х	Х	X	X	Х
dMRI 							X	X

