#### End of Treatment

At the end of the treatment period (when each subject reaches 12 months of age), participants will stop taking the study drug (TAVT-18). Due to the extended half-life of sirolimus, gradual weaning is not necessary. In the absence of significant complications or contraindications, parents who wish to pursue continued treatment with sirolimus after their final study visit as an off-label clinical treatment using commercially-available, FDA-approved medication may do so through consultation with the primary TSC clinician. However, such is not part of the current research study and no research study medication will be provided after completion of the final study visit at 12 months of age.

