### Primary Endpoint Analysis and Statistical Considerations (Efficacy):

The hypothesis is that sirolimus will prevent or delay seizure onset in infants with TSC up to 12 months in age. To evaluate efficacy, we will determine time to seizure onset after treatment initiation in infants treated with sirolimus.

It was originally planned for this analysis to consist entirely of subjects enrolled into Stage 2 (n=60), comparing time to seizure onset between the two groups (treatment vs. placebo). With Stage 2 now eliminated from this protocol, we will instead use a contemporary, prospectively evaluated historical control group (n=32) from our TACERN/TSC-EBS natural history study for comparison (Wu et al. Epilepsia 2019. 60:2428-36), in which infants were similarly enrolled 0-6 months of age and followed until 24 months of age. Instead of time to seizure onset for the comparative analysis, we will use age of seizure onset as the outcome of interest as there was no treatment in the TACERN/TSC-EBS studies to use as a start point. The average age of seizure onset in the TACERN/TSC-EBS control group was 7.4 ±4.4 months. For statistical significance, we will use t-test or Wilcoxon rank sum test for the differences, depending on distribution (parametric vs. nonparametric). In addition, survival analysis will be conducted with statistical comparison between treatment groups utilizing the long-rank test. Seizure frequency, and history of infantile spasms at 12 months of age have been shown to be predictive of long-term neurodevelopmental outcome and seizure control at 24-36 months of age. Therefore, we will similarly compare seizure frequency at 12 months of age using the t-test/Wilcoxon rank sum test and the proportion of subjects who develop infantile spasms (past or current) using Fisher's exact test.

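### Section 16.1 tests age at seizure onset without saying how infants who never seize are counted or at what age the comparison ends; run on observed ages alone, the test would drop the prevention successes

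*Combined protocol and SAP*

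**What the plan says.** The efficacy hypothesis in Section 16.1 is that "sirolimus will prevent or delay seizure onset in infants with TSC up to 12 months in age". With the randomised stage removed, the comparison is with 32 natural-history controls. The outcome becomes age at seizure onset because the controls have no treatment start; that switch is explained. The sentence on inference is "For statistical significance, we will use t-test or Wilcoxon rank sum test for the differences, depending on distribution (parametric vs. nonparametric". A further sentence follows: "In addition, survival analysis will be conducted with statistical comparison between treatment groups utilizing the long-rank test". Neither sentence is named as the main comparison. Nothing gives a value, rank, censoring age or exclusion rule for an infant without a seizure.

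On follow-up, Section 16.1 says of the controls that "infants were similarly enrolled 0-6 months of age and followed until 24 months of age". For treated infants most of the text points to 12 months:
- Section 4.1 lists "Seizure frequency at the end of the treatment period (12 months of age" among the efficacy endpoints.
- Section 8 requires evaluable subjects to "complete the final assessment at 12 months of age".
- In Table 3 the row "Seizure Diary Review" is marked up to the 12-month visit and not at 24 months.
- The End of Treatment part of Section 11.5 says: "At the end of the treatment period (when each subject reaches 12 months of age), participants will stop taking the study drug (TAVT-18".

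However, the Follow-up Visits and Post-treatment follow-up parts of Section 11.5 also collect treated infants' epilepsy history at 24 months. They do not say whether it enters this comparison.

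**The concern.** A preventive drug succeeds by producing infants with no onset age. A test confined to observed ages discards those infants and compares only the treatment failures with the controls who seized. It then has less to work with as prevention improves, and it cannot be run if no treated infant seizes. The plan's benchmark, a control mean of 7.4 ± 4.4 months, makes that reading a natural one, since an average onset age can come only from infants with an onset.

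The unstated age horizon is a second gap. If one cohort's onsets are counted to 12 months and the other's to 24, mean onset ages differ for that reason alone. Section 16.2 keeps significance testing and wants the data to inform later effect-size estimates, so both gaps affect something the plan intends to use.

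**Working it through.** **Plan's own figure.** None to reproduce: Section 16.2 gives no power, effect size or alpha for 5 against 32. A two-sided 5% level is assumed.

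**Inputs from the documents.** 5 treated (Sections 11.2 and 16.2); 32 controls and onset at 7.4 ± 4.4 months (Section 16.1; 4.4 read as an SD); 70% first-year seizure risk (Section 2, a general figure and not one for these 32 controls). Not in the documents, so assumed: how many controls seized, the shape of the onset distribution, and entry ages.

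**1. Best case for the t-test.** Suppose all 37 infants had an onset age. The difference detectable with 80% power is 4.4 × √(1/32 + 1/5) × (1.960 + 0.842) = 5.9 months (6.1 by noncentral t). That is a treated mean of 7.4 + 5.9 = 13.3 months, beyond the 12-month treatment period.

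**2. Missing onset ages.**
- No drug effect: P(at least one of 5 without onset by 12 months) = 1 − 0.70⁵ = 0.832.
- 75% of seizures prevented: treated risk 0.70 × 0.25 = 0.175. P(fewer than 2 onsets) = 0.825⁵ + 5 × 0.175 × 0.825⁴ = 79% (84% at a base risk of 60%, 74% at 80%).
- Hazard ratio 0.25 is a weaker effect: treated risk 1 − 0.30^0.25 = 0.260, so 1 − 0.260/0.70 = 63% are prevented and P(fewer than 2 onsets) = 61%.

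**3. An extreme result.** Take 0/5 treated and 22/32 controls seizing (22 assumed, close to 0.70 × 32 = 22.4). No onset-age test is possible. Fisher's exact test gives C(15,5)/C(37,5) = 3,003/435,897 = 0.007 (0.020 at 19/32, 0.001 at 26/32). Section 16.1 plans Fisher's test only for infantile spasms, but the planned log-rank could be run on these data.

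**4. Simulated power for benefit.** 5 against 32; gamma onset with mean 7.4 and SD 4.4; entry uniform over 0–7 months and seizure-free at entry; 70% of controls seizing by 12 months; both cohorts cut at 12 months. Ranges are across separate runs.

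| Method | HR 0.5 | HR 0.25 | HR 0.1 |
|---|---|---|---|
| t-test, observed ages | 3% | 2–3% | 0.5–1% |
| Log-rank, censored at 12 months | 10–13% | 33–34% | 65–66% |
| Wilcoxon, seizure-free tied last | 15–17% | 39–41% | 69–72% |

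Over control risks of 60–80% the t-test stays at 4% or below, while the log-rank ranges over 10–14%, 24–48% and 46–80%. A different effect model, removing 50%, 75% or 90% of seizures instead of scaling the hazard, gives 4% or less for observed ages on a common horizon and 21%, 50% and 74% for the log-rank.

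**5. Horizon.** With no drug effect, treated onsets to 12 months and control onsets to 24, mean treated onset is about 1.4–1.5 months earlier than control. At equal horizons the difference is 0.0. For a Wilcoxon with seizure-free infants kept, placing treated ones at 12 months and controls at 24 gives power of 4%, 10% and 14% at 50%, 75% and 90% prevention, against 24%, 52% and 76% when both are placed at 12. The log-rank does not change: once treated infants are censored at 12 months none is at risk later, so later control events contribute nothing.

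**6. Where the onset-age test does better.** For a pure 4-month delay with both cohorts cut at 12 months, the t-test has 16–24% power, the log-rank 11%, and the Wilcoxon with ties last 19–21%. With controls run to 24 months the t-test falls to 1–2%.

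**The case against.** The strongest reply is that a suitable analysis is already in the plan. The log-rank is scheduled for the same comparison, and Section 4.1 makes time to seizure onset the primary efficacy endpoint, with age at onset only an additional one. This stands in part. A reader might infer that the efficacy analysis as a whole cannot show prevention; the documents do not support that. What is missing is a statement of which test leads and how seizure-free infants are handled in each.

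The text also never says that only observed ages will be used, and a Wilcoxon can rank seizure-free infants last. That is correct, and the low t-test power is conditional on the observed-ages reading.

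A reader might infer that follow-up is unequal and that the comparison is therefore biased against the drug. The documents do not establish this. Section 11.5 schedules a 24-month visit to check durability, with interval epilepsy history, and Table 3 marks EEG at that visit, so treated onsets could be available to 24 months. The horizon is unspecified, not shown to differ.

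A reader might also infer that the log-rank must be the single main test. The figures do not require it: the Wilcoxon with ties last does slightly better in the cases above.

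Finally, Section 16.2 calls this an unpowered pilot and expects no significance unless the effect is very large, and the randomised question has moved to a separate trial. That limits the stakes. It does not answer the point, because Section 16.2 attributes low power to the small sample, while the loss shown here comes from discarding seizure-free infants and is worst when the effect is largest.

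**Conclusion.** The point holds as a specification gap worth fixing, with modest stakes. Section 16.1 attaches significance to a test of a quantity that seizure-free infants do not have, and gives no rule for them. The 83% chance of at least one missing treated onset age under no effect needs only n = 5 and the 70% risk. On observed ages, t-test power for benefit is about 3% or less at hazard ratios 0.5 to 0.1, against 10–13% rising to about 65% for the log-rank on the same 37 infants. These power values rest on the assumed gamma shape, entry ages and control risk; the ordering held over control risks of 60–80% and under both effect models. It does not hold for a drug that only delays onset.

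The 1.4–1.5 month distortion arises only if treated onsets stop at 12 months and control onsets run to 24, which the plan neither states nor rules out. Correcting these gaps gives a valid pilot comparison and a usable effect estimate; it does not give adequate power.

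**What to change.** In Section 16.1:
- Name in advance one main efficacy comparison that keeps seizure-free infants: either the planned log-rank on the age scale with them censored at 12 months of age, or the planned Wilcoxon with them tied last at 12 months. Drop the t-test on onset age as a significance test.
- State a common 12-month horizon for both cohorts, and say that 24-month histories do not enter this comparison. The horizon matters for the Wilcoxon, the onset-age summaries and the seizure-free proportions; it leaves the log-rank unchanged once treated infants are censored at 12 months.
- Report the 12-month seizure-free probability with a confidence interval in each cohort, and describe onset age among infants who seize without testing it.

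The cost is a few sentences and re-cutting the controls' individual data at 12 months, with no new patients or procedures. The downside is that control events after 12 months go unused, and the log-rank is weaker than an onset-age test if the drug only delays onset.

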The Hypothesis is that sirolimus will be safe and well tolerated in infants with TSC that are 0-12 months of age. Safety is defined as the frequency of severe/life-threating adverse events (grade  $\geq$ 3, Common Terminology Criteria for Adverse Events, CTCAE v5.0) in infants treated with sirolimus compared. Tolerability is defined as the percentage of subjects that discontinue treatment or reduce dose because of an adverse event or serious adverse event (AE/SAE). We will also assess the number of days treatment is held but not discontinued because of an AE/SAE.

*Efficacy*: To demonstrate that sirolimus prevents or delays epilepsy in infants with TSC that are 0-12 months of age.

The Hypothesis is that infants treated with sirolimus before the onset of clinical seizures and continued until 12 months of age. The primary endpoint for efficacy will be time to seizure onset. We will assess efficacy with regards to age at time of seizure onset, seizure type(s), and seizure frequency at the end of treatment (12 months of age) as additional secondary outcome measures, which also have previously been shown to directly correlate with long-term epilepsy severity and neurodevelopmental outcome in TSC.

Additional secondary objectives of the study are:

Version: 7.0 11May2022

- (1) To assess the effect of early sirolimus treatment in TSC infants 0-12 months of age on neurodevelopment and behavior, which closely associate with epilepsy in TSC.
- (2) To assess the effect of early sirolimus treatment in TSC infants 0-12 months of age on TSCassociated electrophysiological (EEG) biomarkers of neuronal connectivity and explore whether normalization of biomarkers is associated with epilepsy prevention and structural biomarkers of neuronal connectivity measured by diffusion MRI (dMRI).
- (3) To optimize treatment with sirolimus in TSC infants 0-12 months of age, identifying dosing that maintains sirolimus trough levels (Cmin) where intolerable side effects are minimized while preserving treatment benefit.

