# **16 STATISTICAL ANALYSIS PLAN**

## 16.1 Data Analysis

## Primary Endpoint Analysis and Statistical Considerations (Safety):

The hypothesis is that sirolimus will be safe in infants with TSC up to 12 months of age. We predict that most AE/SAE will be mild/moderate (CTCAE grade 1 or 2) and as was the case for the treatment of SEGA and epilepsy in TSC,. Descriptive statistics (percentages and 90% CI based on Newcombe's modification of Wilson scores) will be used to describe the frequency of individual AEs by type and severity (CTCAE grade). Treatment tolerability will also be measured as a safety-related endpoint. Tolerability is distinct in that it represents the patient's ability to continue treatment despite the presence of one or more significant or recurrent AEs rather than a measure of the AE frequency or severity itself. Tolerability will be measured as the percentage of subjects that permanently reduce or discontinue treatment because of an AE or SAE. We will also determine the number of days treatment is held but not discontinued because of an AE or SAE. Since this measure of tolerability has no precedent, to our knowledge, there is no non-zero value that we think should or should not be contained within the CI.

There are methodological challenges in safety assessment from a statistical perspective in any clinical trial, especially those that are limited in size or duration. It is no different in TSC,

where every clinical trial evaluating mTOR inhibitors that has led to an FDA-approved indication has reported AE/SAE frequency in descriptive terms without accompanying analysis of statistical significance between groups. Individually and collectively, these studies also have shown that most treatment-related AE and SAE in TSC are mild or moderate in severity. For the current study, we likewise will report all treatment-related AE, by category and severity.

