## 16.2 Study Size and Power Calculations

The original study was powered for the planned enrollment of Stage 2, in which 60 subjects were to be randomized 2:1 for treatment with TAVT-18 (sirolimus) vs. placebo. These power calculations remain valid for STOP2B: TSC-STEPS (CCHMC IRB#2021-0438) that has replaced Stage 2 of the current study. However, with enrollment under the current protocol now limited to Stage 1 only (n=5), this study is no longer powered for definitive analysis and becomes a true pilot study aimed at obtaining preliminary data with regard to potential treatment safety concerns and an estimation of patient variability in treatment response. Analyses for statistical significance will still be carried out with the modifications as outlined above, but it is expected that unless the treatment effect size is very large compared to a similarly matched historical cohort from the TACERN/TSC-EBS study, statistical significance will not be achieved with such a low number of treated individuals in this study. Nonetheless, descriptive analysis as a pilot study using sirolimus (TAVT-18) in a patient population (TSC infants 0-12 months of age) that has hereto never previously been studied in a prospective fashion still has immense scientific and clinical value. Furthermore, should the TAVT-18 sirolimus formulation be further developed as a potential clinical treatment for this indication, the descriptive statistics will provide essential data for estimating potential treatment effect size and interpatient variability values that will prove essential for determining study size and study power.

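### Section 16.1 tests seizure onset by two parallel methods, plus two further endpoints, without an alpha or a deciding test, and leaves open how seizure-free infants enter the onset-age test

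*Combined protocol and SAP*

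**What the plan says.** The efficacy part of section 16.1 states one hypothesis, about preventing or delaying seizure onset. The untreated historical cohort has no treatment start, so the section moves from time to onset to age at onset: "we will use age of seizure onset as the outcome of interest". It then plans four comparisons of 5 treated infants with 32 controls:

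1. Onset age: "For statistical significance, we will use t-test or Wilcoxon rank sum test for the differences, depending on distribution (parametric vs. nonparametric").
2. Onset by survival analysis: "In addition, survival analysis will be conducted with statistical comparison between treatment groups utilizing the long-rank test".
3. Seizure frequency at 12 months, by t-test or Wilcoxon.
4. Infantile spasms, by Fisher's exact test. Items 3 and 4 share one sentence, quoted here in part: "we will similarly compare seizure frequency at 12 months of age using the t-test/Wilcoxon rank sum test and the proportion of subjects who develop infantile".

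The endpoints are ranked differently elsewhere. Section 4.1 says: "The primary endpoint for efficacy will be time to seizure onset, when treated with sirolimus (TAVT-18). Additional efficacy-related endpoints include" onset age, infantile spasms and seizure frequency, all under the heading Primary Endpoints. The abstract lists age at onset, seizure type and "seizure frequency at the end of treatment (12 months of age) as additional secondary outcome measures". Section 9.2 also calls seizure type and frequency secondary.

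Section 16.2 says the study is a pilot and is not powered for definitive analysis, yet "Analyses for statistical significance will still be carried out with the modifications as outlined above". The only confidence level in section 16.1 belongs to safety: "Descriptive statistics (percentages and 90% CI based on Newcombe's modification of Wilson scores").

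**The concern.** Two tests address the same onset question, and the plan does not formally say which one a significance statement would rest on. Two more p-values on other endpoints sit under the primary heading with no exploratory label. Section 16.2 leaves room for significance if the effect is very large, but does not say on which test.

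The two onset tests are also not interchangeable. A log-rank test keeps a seizure-free infant as a censored observation. A t-test or Wilcoxon on onset age needs a number for every infant, and a seizure-free infant has none. The plan does not say whether such infants are left out or given a value. Since the hypothesis includes prevention, these infants carry much of the information.

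**Working it through.** **No figure to reproduce.** The documents give no alpha, power or error rate for 5 versus 32. Two-sided 5% per test is an assumption throughout.

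**Inputs from the documents.** 5 treated infants (16.2), 32 controls (16.1), and 70% with seizures in the first year (section 2).

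**Inputs assumed.** Exponential onset; spasms in about 65% of infants with seizures; seizure frequency zero if seizure-free and skewed otherwise; correlation between outcomes of 0, 0.5 or 0.8.

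**Step 1: simple bounds.** For k independent tests the chance of at least one false positive is 1 − 0.95^k.
- Two tests: 1 − 0.95² = 9.75%.
- Four tests: 1 − 0.95⁴ = 18.55%.
- With equally correlated normal tests, two give 9.1% at correlation 0.5 and 7.0% at 0.9. Four give 15.6% and 9.5%.

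**Step 2: the actual tests under no effect, 5 versus 32, by simulation.** The ranges cover the correlations, both ways of handling seizure-free infants (left out, or entered at 12 months), and the log-rank in its ordinary form or calibrated to 5%. One test is used on onset age at a time, and seizure frequency is tested by Wilcoxon.

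| Family | Either direction | Favouring sirolimus |
|---|---|---|
| One test, nominal | 5% | 2.5% |
| Two onset tests | about 6-11% | about 2-4% |
| All four | about 9-15% | about 4-6% |

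With a t-test on the skewed frequency instead, and a different spasm assumption, the four-test figure reached 16.6%. The ordinary log-rank alone rejects in about 6-7% of null trials, because one group has five infants. Fisher's test is conservative, at 1.8-3.0% for spasm rates of 20-60%.

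**Step 3: seizure-free infants.** With 70% having seizures by 12 months, 30% have no onset age. That is 5 × 0.3 = 1.5 treated infants and 32 × 0.3 = 9.6 controls if the drug does nothing.

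Suppose a true hazard ratio of 0.3. The chance that a treated infant is seizure-free at 12 months becomes 0.3^0.3 = 0.697, so about 5 × 0.697 = 3.5 of the 5 are seizure-free and 1.5 have an onset age. The chance that none or one of the five has a seizure is 0.697⁵ + 5 × 0.303 × 0.697⁴ = 0.164 + 0.358 = 0.52.

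With one treated infant against k controls, the smallest exact two-sided Wilcoxon p-value is 2/(k + 1). Even at k = 32 this is 2/33 = 0.061. So in about half of such trials an exact Wilcoxon restricted to infants with seizures cannot reach 5%.

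**Step 4: power at hazard ratio 0.3, by simulation.**
- Wilcoxon on onset age, infants with seizures only: about 3%.
- Ordinary log-rank: about 28%. Calibrated to a true 5%, it falls to about 21%.
- Wilcoxon with seizure-free infants entered at 12 months: about 34%.

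When at least one onset test is significant at this hazard ratio, the other is not in 99% of cases if seizure-free infants are left out, and in 26% if they are entered at 12 months (ordinary log-rank).

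**The case against.** Much of the case on the other side stands.

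- **Informal order.** Section 16.1 ties the t-test or Wilcoxon to significance and brings in the log-rank as an addition. That is an order of sorts. But the test it favours is the one that has no value for seizure-free infants, while section 4.1 names a time-to-event endpoint.
- **One hypothesis tested four ways.** A reader might infer this, with an error rate of up to 16%. The documents do not support it. The stated hypothesis concerns onset, which only two tests address. Frequency and spasms come in with their own rationale, as predictors of later outcome. Section 16.1 also picks one of t-test and Wilcoxon by distribution, so they are not two chances on onset age.
- **False claims of benefit.** The two-directional figures overstate this risk. For the onset pair, false results favouring sirolimus run at about 2-4% against 2.5%, so inflation there is small or absent.
- **Pilot status.** A reader might infer that a chance p-value would drive later development. Section 16.2 instead rests planning on descriptive statistics, and the randomised comparison has moved to a separate protocol.
- **Disagreement between tests.** One significant and one non-significant result are not opposite findings. The 99% comes from leaving out seizure-free infants, not from multiplicity.
- **Change of time scale.** Moving to age at onset is explained in the text and is not an error.

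**Conclusion.** The point holds in a limited form. The plan has several unadjusted significance tests, no alpha or sidedness, no formal deciding test, and endpoint ranks that differ between sections 4.1, 9.2, 16.1 and the abstract. The inflation is modest, and it rests on an assumed 5% level and on assumed correlations, onset distribution and spasm rate. It should be read as a range, and not as a departure from a rate the plan claims.

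The handling of seizure-free infants matters more. Left out, they reduce the onset-age comparison to almost no ability to show prevention. Entered at 12 months, the Wilcoxon does at least as well as the log-rank in this model. The case for the log-rank is therefore not power alone. It matches the time-to-event endpoint in section 4.1 and states openly how seizure-free infants count. The choice changes what the trial can report, but no confirmatory decision depends on it.

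**What to change.** In section 16.1:
- State alpha and sidedness for efficacy.
- Make a time-to-event comparison on the age scale through 12 months, with seizure-free infants censored, the only comparison on which a significance statement about prevention or delay rests. The common 12-month limit is needed because the controls were followed to 24 months.
- Use an exact or permutation log-rank p-value, since the ordinary test exceeds 5% at 5 versus 32.
- Label the t-test or Wilcoxon on onset age a sensitivity analysis, and say how seizure-free infants enter it.
- Report seizure frequency and infantile spasms as exploratory estimates with confidence intervals.

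Then align sections 4.1, 4.2, 9.2, 16.1 and the abstract, for example by moving the three additional efficacy items from 4.1 to 4.2.

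The cost is a few sentences and no new data, patients or procedures. The sponsor gives up significance claims on the other three comparisons. Correcting the log-rank to a true 5% also lowers its power, from about 28% to about 21% at a hazard ratio of 0.3 in the model above.
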